### C. Study Design

#### C1. Overall Design/Clinic Selection/Clinic Enrollment

We will use a randomized controlled trial design with staggered-entry and a waitlisted control group to compare the effectiveness of an alert and registry-driven CHW-led coaching compared with usual care among patients with HbA1c at  $>7\%$ . Randomization will be at the individual-level and stratified by PCP, meaning eligible treatment and control participants will be randomized for each PCP. PCPs will be clustered into waves, aligning with the original stepped-wedge design. Entry into the study will be staggered in three waves, with each wave consisting of six to seven PCPs (See Figure 1). All 20 PCPs will be recruited and enrolled by month 6 of Year 1 (study period 6, Figure 1), and we will assign 6-7 practices into each of the 3 waves upon enrollment. For each PCP, there will be a total of two rounds of consecutive six-month CHW intervention periods for the treatment group: 1 month for recruitment and enrollment of treatment participants and five months of community health worker-led group education sessions (approximately one session per month). Data related to the study outcomes will be extracted from EHR systems a total four times (baseline, 6 month, 12 month, and 18 month) for each PCP; we will be comparing EHR data from 443 treatment participants with 443 control participants. Prior to allocation into treatment group, each treatment participant will be matched to a control participant based on age, gender, and BMI. Treatment participants will be split into two groups and assigned to either first or second round. All control participants will be waitlisted during the first round and will be offered the full CHW group education sessions during the second round as a point of service (i.e., not for research purposes).

Randomization at each PCP will occur during the first round. PCPs will be placed into waves based on geographic location and CHW caseload considerations. PCPs will be eligible for participation if they have a) an overall patient volume of  $N \geq 1000$  ; b) at least 70% of the patient population is South Asian; and c) the practice has used EHR for at least 12 months. All PCPs will sign a Memorandum of Understanding (MOU) between the PCP and NYU outlining study commitments.

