#### *1. Data collection and consenting with treatment participants*

Patients assigned to the treatment group will be sent an invitation letter to participate in the CHW intervention (See *Recruitment Letter for CHW Intervention*). Invitation letters will be followed up with phone calls by CHWs (See *Script for Telephone Screening for CHW Intervention*). In addition, a screening form (See *Telephone Screening Form for CHW Intervention*) will be completed to verify eligibility. CHWs will call patients a maximum of 10 times over a two-week period at varying times of day to screen and invite them to enroll into the study.

The CHW intervention includes a protocol that consists of 5 monthly 90-minute group health education sessions, providing the tools and strategies to manage diabetes. All sessions employ adult learning techniques and group-based learning and activities. All session materials have been culturally and

linguistically adapted into Bengali, Urdu, Hindi, Punjabi, and Nepali. Sessions will be held remotely via audio phone calls via telephone, MCIT approved Zoom or Webex platforms, remote sessions will be conducted for the community health worker intervention as a result of the current COVID-19 pandemic. Remote sessions are preferred due to limited ability to properly socially distance in the small offices of the participating PCP clinics and community organizations. When clinic restrictions and limitations due to COVID-19 have been lifted, a modification to the protocol will be submitted and in person health education sessions will resume as initially underlined in the protocol. In that circumstance sessions will be implemented in PCP clinics and, community spaces identified by partner agencies or at private residences with approval from tenants.

Patients will also receive 2 one-on-one phone calls from CHWs to discuss individualized challenges, strategies, and action plans for diabetes management and referral to community resources. The tested curriculum also incorporates a family-centered approach; for example, family members are invited to attend sessions and participate in one-on-one calls.

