## B. Data Analysis and Data Monitoring

### B1. Aim 1 Analysis

AIM 1: Specific Aim I: Test the effectiveness of a multi-level diabetes management intervention compared to usual care. The primary outcome is reduction in HbA1c for patients with baseline HbA1c of >7%. The secondary outcomes include enhanced use of community and social services and increased self-efficacy.

*Hypothesis:* Individuals receiving the multi-level diabetes management intervention will be more likely to achieve >0.5% reduction in HbA1c 6 months following the index office visit than individuals receiving care as usual.

The analysis of the effect of intervention on the outcome measure will proceed using a Generalized Linear Mixed Model (GLMM). In particular, we will use a random effects model that assumes a binomial distribution with a logit link function. The comparison will make no linear assumption about the time trend for each outcome over the course of the trial. The model will be as follows:

$$(1) \quad \text{logit}(Y_{ijt}) = \mu + \alpha_j + \theta_t + \tau C_i,$$

where  $Y_{ijt} = 1$  if the  $i^{\text{th}}$  subject attached to the  $j^{\text{th}}$  clinic at time quarter  $t$  achieves an HbA1c reduction of 0.5% or more within six months following the index visit,  $Y_{ijt} = 0$  otherwise.  $\alpha_j$  is a random effect for clinic  $j$  with mean 0 and variance  $\sigma^2_b$ .  $\theta_t$  is a time-specific effect of quarter  $t, t \in (1, 2, \dots, 12)$ .  $C_i$  is an indicator variable, and  $C_i = 1$  if individual  $i$  receives care under the EHR/CHW intervention,  $C_i = 0$  if individual  $i$ .  $\tau$  represents the treatment effect of the intervention. The model will be fit using the LME4 package using R software. The hypothesis will be tested using two-sided level of significance  $\alpha = .05$ . Because outcome data will be derived from administrative data, we do not anticipate missing data. However, in the event that there is missing data, we will use multiple imputation under the assumption of data missing at random (MAR). This is consistent with following an intent-to-treat protocol. Sex as a biological variable will be addressed by exploring gender as a potential moderator of intervention effects.

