### **Power Calculation:**

We conservatively estimate a 10% difference in effect size (i.e.,  $\geq 0.5\%$  reduction in HbA1c) comparing treatment and control group participants. Accrual of 886 participants, evenly randomized to treatment or control groups, provide greater than 80% power to detect this difference, using a 2-sided, 0.05-level test (i.e., 44 participants (22 treatment and 22 control participants per PCP). These calculations assume 15% loss to follow-up and enrollment of 20 PCPs.

**Sampling.** Preliminary data from our practice needs assessment indicates that approximately 375 unique patients for every six months will have an office visit. Based on our past research, we estimate 40% of those individuals will have a Type II Diabetes diagnosis ( $n=150$ ), and conservatively estimate that only 40% will meet our eligibility criteria for the study ( $n=60$ ). In our previous diabetes management CHW intervention among South Asians, screening to enrollment rate is 41%. For this study, we apply a similar estimate that 40% of patients will be interested in the study and will be contacted by a CHW ( $n=24$ ). Based on retention rates from our CHW studies we estimate that approximately 90% of individuals in control and treatment quarters will be followed up at six months ( $n=22$ ). Thus, for each clinics, we will enroll approximately 22 patients every six months over a period of one year, resulting in total recruitment of approximately 886 participants across 20 clinics. Thus, approximate CHW caseload over a six-month period is 22 participants (about 4 patients per month for a part-time CHW), consistent with caseloads from our previous studies.

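### The primary model has no term for group-delivered treatment, so the standard error of the treatment effect is too small if outcomes within CHW session groups are positively correlated

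*Combined protocol and SAP*

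**What the plan says.** Section C1 randomizes individual patients, stratified by PCP, and splits each PCP's treated patients between two consecutive six-month rounds. On delivery, section C2 says: "The CHW intervention includes a protocol that consists of 5 monthly 90-minute group health education sessions". Treated patients also receive individual CHW calls. Controls are waitlisted in round 1 and are offered the full group sessions in round 2 as a service.

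For the primary outcome (HbA1c reduction of 0.5% or more), section B1 says: "we will use a random effects model that assumes a binomial distribution with a logit link function". Model (1) contains a constant, a random intercept for clinic, a fixed effect for quarter and the treatment indicator with coefficient tau. It has no session-group, CHW or clinic-by-arm term, and no robust variance is mentioned.

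The power paragraph reads: "We conservatively estimate a 10% difference in effect size". It adds: "Accrual of 886 participants, evenly randomized to treatment or control groups", and says that these "provide greater than 80% power to detect this difference", "using a 2-sided, 0.05-level test". It continues: "These calculations assume 15% loss to follow-up and enrollment of 20 PCPs". It gives no ICC, design effect or control rate.

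**The concern.** In round 1 this is a partially nested design. Treated patients share sessions, peers and a CHW, while controls are independent apart from their clinic. Each clinic contributes about equally to both arms, so the clinic intercept is common to the two sides of the comparison and largely drops out of tau. It cannot absorb variation between treated groups.

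If that variation exists, model (1) treats the treated patients as more informative than they are. The confidence interval for tau is then too narrow and the primary test rejects too often. The planned sample size carries no allowance for it either. With a positive correlation the error always runs toward a falsely positive primary result.

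**Working it through.** **1. Inputs from the documents.** Two-sided alpha 0.05; 443 per arm; 15% loss; 20 PCPs; 22 treated and 22 control patients per PCP; two treatment rounds per PCP.

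**2. Assumptions, because the documents give no figure.** ICC 0.01 to 0.05 (also 0 and 0.10); one session group per PCP and round; control rate 30% or 35%; the 10% difference read as 10 percentage points.

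**3. The plan's own figure.** Two proportions, pooled variance, no design effect: 35% v 45% needs 376 evaluable per arm for 80% power, and 376/0.85 = 442.4, rounded up to 443. With a continuity correction, 30% v 40% also gives 376 and then 443. The control rate is therefore not identified, but both matches are independent-observations calculations. With 376 per arm, power is 88.8% at 20% v 30%, 82.1% at 30% v 40%, 80.0% at 35% v 45% and 78.4% at 45% v 55%.

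**4. Group size.** Completers per PCP-and-round group: 22 × 0.85 / 2 = 9.35. If clustering acts per PCP or CHW: 22 × 0.85 = 18.7.

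**5. Size by formula (ICC on the proportion scale).** The design effect applies in the treatment arm only: DE = 1 + (m − 1) × ICC. The ratio of true to reported standard error is sqrt((1 + DE)/2). Type I error is 2 × (1 − Φ(1.96/ratio)).

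| m | ICC | DE | SE ratio | Type I error |
|---|---|---|---|---|
| 9.35 | 0.01 | 1.08 | 1.02 | 5.5% |
| 9.35 | 0.02 | 1.17 | 1.04 | 6.0% |
| 9.35 | 0.05 | 1.42 | 1.10 | 7.5% |
| 18.7 | 0.01 | 1.18 | 1.04 | 6.0% |
| 18.7 | 0.02 | 1.35 | 1.08 | 7.1% |
| 18.7 | 0.05 | 1.89 | 1.20 | 10.3% |

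**6. Simulation of the planned type of model.** Logit mixed model with one clinic intercept and a fixed period effect; 20 clinics; 19 + 19 followed per clinic; 30% rate in both arms; clinic ICC 0.02; group effects in the treatment arm only; 2,000 runs per scenario. Monte Carlo error is sqrt(0.05 × 0.95/2000), about 0.5 points. Type I error by ICC on the latent (logit) scale:

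| Treated groups per clinic | ICC 0 | 0.01 | 0.02 | 0.05 | 0.10 |
|---|---|---|---|---|---|
| 2 | 5.1% | 5.3% | 6.1% | 6.6% | 7.9% |
| 1 | – | 4.9% | 5.9% | 8.0% | 10.4% |
| 4 | – | – | 5.1% | 5.6% | 6.4% |

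The simulated values are milder than the formula, probably in large part because of scale. A latent ICC of 0.05 means a between-group variance of (0.05/0.95) × π²/3 = 0.173. At a 30% rate that is about 0.30 × 0.70 × 0.173 = 0.036 on the proportion scale.

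**7. Power with a correct standard error.** SE = sqrt([p1(1 − p1) + DE × p2(1 − p2)]/n), with n = 443 × 0.85 = 376.55; power = Φ(0.10/SE − 1.96). For m = 9.35 and ICC 0.01, 0.02, 0.05:
- 35% v 45%: 79%, 77%, 72%.
- 30% v 40%: 81%, 79%, 74%.

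At ICC 0 the same formula gives 80.4% and 82.5%; the small difference from step 3 is the unpooled variance.

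**The case against.** A reader might infer that the test's type I error exceeds 5% as a matter of fact. The documents do not support that: they give no ICC, and at ICC 0 the simulated rate is 5.1%. At latent ICC 0.01 the result cannot be told apart from 5%. Moreover, with individual randomization and no effect on any patient, shared sessions cannot change outcomes, so they add no correlation. Inflation needs group effects that vary but average zero. This stands, and it makes the point conditional. It does not rescue the interval: if the intervention works better in some groups than others, model (1) still understates the uncertainty in tau.

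It is also tempting to say that grouping occurs in the treatment arm only throughout the trial. Section C1 offers controls the same sessions in round 2, so this holds cleanly only for the round-1 contrast. Later attendance by controls adds further unmodelled clustering; it does not justify model (1).

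Group size is not fixed. Section C2 offers several session times, remote delivery, materials in five languages and individual calls, so groups may be smaller than 9. With four groups per clinic the simulated rate is only 5.1% to 5.6% at ICC 0.02 to 0.05. That stands as a limit on the size. Patients may nevertheless share a CHW, which would act at a larger cluster size.

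The power loss depends on an undocumented control rate. At 30% v 40% and ICC 0.01 the stated power survives.

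**Conclusion.** The omission is established; its size is not. The treatment arm is nested in CHW-led groups, model (1) has only a clinic intercept common to both arms, and nothing else in the plan deals with this. Any positive group or CHW correlation biases the standard error of tau downward.

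Under the stated assumptions (about 9 completers per group, ICC 0.01 to 0.05) the true standard error is about 2% to 10% larger than reported. Type I error is then roughly 5.3% to 7.5%, depending on the scale of the ICC. It is about 5% to 10% with about 19 per cluster, and close to 5% if the ICC is near zero or groups are small. At ICC 0.01 to 0.02 in groups of about 9, the excess is about one point or less. The power claim holds as an independent-observations figure and has little or no room for clustering.

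This should be changed because the correction is cheap and needs no ICC value. It is not evidence that the planned test is badly invalid.

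**What to change.** 1. **Record the identifiers.** Record session-group and CHW identifiers for every treated patient, using the assigned group so that intention-to-treat is kept. The EHR fields listed in section A2 include clinic and patient identifiers but neither of these. The study's own records of consented treatment participants are a natural place for them.
2. **Change model (1).** Add a random effect that acts only in the treatment arm, at the level where delivery is actually shared: session group, plus CHW or a clinic-by-arm random slope. In lme4, with arm coded 0/1, the group term is `(0 + arm | group)`. A PCP-by-round term alone is not enough, because it treats a PCP's two rounds as independent and misses a CHW or PCP effect common to both. Alternatively, use a standard error robust to clinic-by-arm clustering with a small-sample correction for 20 clinics.
3. **Restate the power.** Give the control rate, the group size and an ICC range with the matching power.

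The cost is a slightly wider interval, slightly lower stated power and additional identifiers to record. If the group variance is near zero, the result is almost unchanged.

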### *CHW Intervention*

Inclusion Criteria: Participants will be eligible for study participation if they meet the following criteria: a) are of South Asian ethnicity; b) are at least 21 years of age and younger than age 75, c) had an appointment with a physician or mid-level clinician for routine non-emergent primary care in the last 12 months; d) a diagnosis of diabetes and e) an HbA1c reading of >7 in the last 12 months.

Exclusion Criteria: Patients under the age of 21 and older than 75 will be excluded. Pregnant women and all visits with an obstetrician gynecologist are excluded. Patients will be excluded if they were enrolled in a CHW led hypertension or diabetes education intervention in the past five years.

No children or vulnerable subjects will be enrolled in this study.

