## **VI. SUBJECT IDENTIFICATION, RECRUITMENT, AND CONSENT/ASSENT**

### **A. Method of Subject Identification and Recruitment**

#### *Treatment participants for CHW intervention*

Patients that meet eligibility criteria will be drawn from registry lists and randomized to treatment or waitlisted control. Patients assigned to the treatment group will be sent an invitation letter (See *Recruitment Letter for CHW Intervention*) to participate in the CHW intervention. Invitation letters will be followed up with phone calls by CHWs (See *Script for Telephone Screening for CHW Intervention*), during which CHWs will explain the study and elements of informed consent. Participant names, telephone numbers, and email addresses will be needed in order for CHWs to contact participants regarding participation in the intervention (Please see *Application for Waiver of Authorization for Telephone Screening Form*). In addition, a screening form (See *Telephone Screening Form for CHW Intervention*) will be completed to verify eligibility. CHWs will call patients a maximum of 10 times over a two-week period at varying times of day to invite them to enroll into the study.

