### **B. Process of Consent**

All study personnel will have completed the mandatory CITI human subjects research training before commencing any study-related activities.

The informed consent form for this study have been created by the NYU Grossman School of Medicine Office of Science and Research in accordance with Federal guidelines, including the Health Insurance Portability and Accountability Act (HIPAA). A verbal consent will be obtained via telephone from participants (see *Waiver of Authorization and Documentation of Consent* and *Telephone Consent Form*). A verbal consent is preferable due to the 1) remote nature of the intervention 2) the South Asian immigrants have limited technological literacy and are unable to complete an electronic consent via REDCap as this will also require them to have email accounts which are used sparingly in this population. The CHW will review all the elements of informed consent over this call and (see *Telephone Consent Form*) will offer to provide a key information page subsequently, (see *Key Information (Patients)*) via text message(See *Text Message Script*). Texts will be sent from a secure NYULMC phone A log of consented treatment participants will be stored on REDCap.

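### The primary outcome is timed from an undefined index visit that registry-based entry does not supply, so its six-month window is not tied to randomisation

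*Combined protocol and SAP*

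**What the plan says.** Section III.B1 (Aim 1 Analysis) states the clock twice. The hypothesis runs, in part, "reduction in HbA1c 6 months following the index office visit than individuals receiving care as usual". The definition of Y gives the value 1 to a patient whose HbA1c falls by at least 0.5% "within six months following the index visit". The index visit appears nowhere else in the document.

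Entry is described differently. Under section VI.A, "Patients that meet eligibility criteria will be drawn from registry lists and randomized to treatment or waitlisted control". The inclusion criteria in section II require that the patient "had an appointment with a physician or mid-level clinician for routine non-emergent primary care in the last 12 months" and has "an HbA1c reading of >7 in the last 12 months". Treatment patients are contacted only after assignment, and under section VI.B "A verbal consent will be obtained via telephone from participants". Sections I.C2 and VI.G say that controls contribute EHR data only and have no research contact with study staff.

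Section I.C1 gives each practice two consecutive six-month rounds, each made up of "1 month for recruitment and enrollment of treatment participants and five months of community health worker-led group education sessions". Randomisation takes place during round 1. Treatment participants are divided between the two rounds, and controls are offered the sessions in round 2.

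**The concern.** A randomised comparison needs a time zero that is fixed at or after assignment and set in the same way in both arms. An index visit would serve if patients entered at a visit. Here they enter from a list, so an analyst has to choose a visit, and the plan does not say which.

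- **A visit before randomisation.** HbA1c change before assignment cannot be affected by assignment. Counting it pulls the treatment difference towards zero.
- **The first visit after randomisation.** The start of follow-up is then itself a post-randomisation event. Only the treatment arm is contacted by community health workers (CHWs), so visit timing may differ by arm and the bias could go either way.

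Two analysts could therefore derive different primary outcomes from the same records. The listed de-identified extract (section III.A2) dates diagnoses, height and weight, and laboratory results by month and year, but lists no office-visit date.

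**Working it through.** **Plan's own figure.** The power statement gives 886 participants, 1:1, a 10-point difference, two-sided 0.05, 15% loss and power above 80%. Evaluable per arm: 443 × 0.85 = 376.55, taken as 376. The control response rate is not stated. The two-proportion formula with pooled variance under the null is

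power = Φ{[d√n − 1.96√(2p̄(1−p̄))] / √(p₁(1−p₁) + p₂(1−p₂))}.

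With n = 376 and d = 0.10, this gives 88.8% for 20% vs 30%, 82.1% for 30% vs 40%, 80.0% for 35% vs 45% and 78.4% for 45% vs 55%. The stated figure is reproduced for control rates up to about 35%. It contains no allowance for a window that misses the intervention.

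**Single records, literal reading.** Put randomisation at month 0 and round 1 sessions in months 1 to 6.

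- Visit at month −8: the window closes at −8 + 6 = −2, before assignment.
- Visit at month −3: the window closes at −3 + 6 = 3, after about 2 of 5 session months.
- First visit after randomisation at month 4: the window closes at 4 + 6 = 10. Round 2, when controls are offered sessions, begins at month 6.

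**Average coverage if the index visit is the qualifying visit.** Assume visits are uniform over a look-back of L months before randomisation, with u the age of the visit.

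- Window wholly before randomisation: P(u ≥ 6).
- Share of window after randomisation: mean of max(6 − u, 0)/6.
- Session months covered: mean of max(5 − u, 0).

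| L (months) | Wholly before | Share after | Session months, of 5 |
|---|---|---|---|
| 3 | 0% | 75% | 5 − 1.5 = 3.5 |
| 6 | 0% | 50% | 12.5/6 = 2.1 |
| 12 | 50% | 25% | 12.5/12 = 1.0 |

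**Illustrative power.** Assume also that the 10-point difference shrinks with the share of the window after randomisation, which is the milder of the two scalings. With 376 per arm and a 30% control rate (range for 20% to 45% in brackets):

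- 7.5 points: 58.5% (67.7% to 53.9%)
- 5 points: 31.0% (37.5% to 27.8%)
- 2.5 points: 11.1% (13.1% to 10.2%)

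**Check on the obvious repair.** If everyone is scored six months from randomisation, round 1 participants have all 5 session months in the window. Round 2 sessions fall in months 7 to 12, so those participants have 0 of 5. One randomisation date for all would therefore bring in a new fault.

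**The case against.** The strongest reply is that the surrounding text plainly points to follow-up after entry. Section III.A2 calls for HbA1c at a routine office visit at six months, with CHW calls and travel incentives where no visit is booked. Section I.C1 schedules extractions at baseline, 6, 12 and 18 months per practice. Sections I.C2 and VI.G place the treatment-arm survey about six months after the intervention starts. No section equates the index visit with the qualifying visit, and a window that closed before randomisation would sit badly with all of these.

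Most of this stands. It shows that a pre-randomisation window is permitted, not that it was intended. It also means the qualifying visit is not the only office visit in the plan. It does not settle the matter, because none of these sections redefines Y. The six-month visit has no stated starting point, the extractions are counted per practice, and the survey covers one arm.

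A reader might also blame telephone consent. It only confirms that there is no entry visit. The cause is registry entry combined with a look-back twice as long as the outcome window.

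**Conclusion.** The concern holds as a defect of definition: the primary-outcome clock is tied to an event that the design neither supplies nor defines. The wording appears to be carried over from a visit-based design. Section I.C1 refers to an original stepped-wedge plan, and the sampling text still counts office visits and speaks of control and treatment quarters.

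A reader might infer that the outcome is settled before randomisation for half the patients, or that true power is near 10%. The documents do not support that. Those figures need the index visit to be the qualifying visit, visits spread evenly over the full 12 months, an effect proportional to the window covered, a control rate the plan does not give, and all sessions in the first six months. With a 3-month look-back, 3.5 of 5 session months are still covered. A patient seen close to randomisation loses almost nothing. The coverage and power figures show direction and possible scale only. The need for a stated time zero does not depend on them.

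**What to change.** In section III.B1, replace both references to the index visit with one assigned calendar date that depends on no visit and is the same in both arms:

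- Round 1 treatment participants and their matched controls: the date the practice's list is randomised.
- Treatment participants assigned to round 2: the start of that round, with the same date given to their matched controls. Controls are offered sessions in round 2, so that overlap has to be reconciled separately.

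Take baseline as the last HbA1c on or before the assigned date. Score Y on the HbA1c nearest six months after it, within a stated window. State that window in whole months, since laboratory dates are held as month and year. Set the time effect in the model to the quarter of the assigned date.

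The cost is mainly wording, to be settled before outcomes are analysed, with the assigned date recorded for each matched pair. The downside is that baseline readings will vary in age in both arms: up to 12 months at randomisation, and up to about 12 + 6 = 18 months at a round 2 start if no newer reading exists. The planned sample size does not change.
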